12.6. Performance, Functional and Other Endpoint Analysis

The device success, procedural success, and clinical success will be summarized by counts and percentages for the implanted population. NYHA performance will be assessed at baseline, 1 month, 6 months, and annually up to 5 years. The distribution (numbers of patients and percentages) in the various NYHA classes will be tabulated at baseline, 1 month, 6 months, and annually up to 5 years. Echocardiographic performance data will be obtained at the following time points: baseline, 1 month, 6 months, and annually up to 5 years. Descriptive statistics such as mean, standard deviation and range will be calculated for the continuous echo variables as well as the change from baseline for each variable.

Change in overall (general) quality of life will be measured through the use of health status questionnaires (e.g., KCCQ) and a six-minute walk test. QoL metrics will be assessed at 1 month, 6 months, and annually for 5 years from the implant procedure.

The average overall (general) quality of life changes at baseline, 1 month, 6 months, and annually for 5 years and the changes from baseline to follow up will be summarized by mean and standard deviation for the implanted cohort. Patients that are missing a baseline or follow up values will be excluded from the analysis.

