12.8. Missing Data

All statistical analyses will be performed using only those patients with available data required for endpoint analysis.

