### 6. DATA AND ANALYSIS CONVENTIONS

#### 6.1 General Conventions

For continuous variables, results will be summarized with the number of observations, mean, standard deviation, median, minimum, maximum, and 90% confidence interval (CI) by normal approximation. For categorical variables, results will be summarized with patient count, percentage, and 90% CI by normal approximation, where appropriate.

Survival analysis techniques will be used to analyze time-to-event variables. Patients without events will be censored at their last participation date in the study. For patients who did not have an event but remain in the study, they will be censored at the database extract date. Time to first event curves will be constructed using Kaplan-Meier estimates. Descriptive statistics will be presented at each assessment, including change from baseline to subsequent time point for selected endpoints. For the determination of event rates, the number of patients in the patient population who have had the events or have been followed up to the upper bound of the follow-up visit window will be used as the denominator. Unless otherwise noted, patients with missing data will be excluded from the denominator.

When the sample size is small (e.g., <10 patients), analysis may be performed in the form of listings only.

Quality of life questionnaires will be scored according to algorithms provided by the vendor. The various summary scores produced by the algorithms will be analyzed as continuous variables.

Unless otherwise specified, confidence limits will be two sided, using alpha = 0.05.

Unless otherwise specified, the precise form of each algorithm will be the default of SAS, using the latest release installed at Edwards Lifesciences (Edwards) at the time of analysis.

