#### 6.2 Handling of Missing Data

For AEs with partial onset dates, if the year is not missing, imputation will be performed by finding the earliest possible date on or after the index procedure. If the year is missing, no imputation will be performed.

E	Revision Date: August 1, 2022		Rev		For Use Only by Affiliates of Edwards Lifesciences	Page 13 of 18
Edwards	Title	Statistical Analysis P	lan foi	r TRIS	CEND Study	v (2019-06)

For endpoint-related AEs (such as MAEs) with partial dates, in addition to applying the imputation method above, the sponsor will review the events and related records on a case-by-case basis, and manually verify the imputed dates. All imputations will be documented and filed in the Trial Master File (TMF).

For missing data due to patient withdrawal or lost to follow-up in the analyses of time-dependent endpoints, the patients will be censored on the last participation date as stated above.

Unless otherwise specified, all statistical analyses will be performed using only those patients with available data required for endpoint analysis, and no other missing value imputation will be performed.

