## 8.4 Clinical and Functional Endpoints and Parameters

The clinical and functional endpoints and parameters will be presented in the AT population.

All-cause mortality rates, heart failure hospitalization rates, and non-elective tricuspid valve re-intervention (percutaneous or surgical) rates at 12 months and annually thereafter and the corresponding 95% confidence intervals will be computed using Kaplan-Meier estimates with the standard errors being computed using Greenwood's formula.

Volume overload assessed by serial measurements will be summarized at each timepoint using descriptive statistics.

NYHA class will be assessed at baseline, 1 month, 6 months and annually up to 5 years. The distribution (numbers of patients and percentages) in the various NYHA classes will be tabulated and plotted for each timepoint.

Change from baseline in NYHA class, body weight, ankle circumference measurement, and edema assessment will be presented as shift from baseline for each of the pre-specified follow-up periods. Paired t-test (for continuous data) or Wilcoxon signed-rank test (for categorical data) will be performed comparing the following timepoint with the screening/baseline data. Patients who are missing a baseline or follow-up value will be excluded from the paired analysis.

Quality of life (KCCQ, SF-36v2) and functionality (6MWT) measurements will be summarized at each visit using descriptive statistics. Change from baseline at corresponding follow-up visits will be summarized by mean and standard deviation. Patients who are missing a baseline or follow up values will be excluded from the analysis. For the analyses of 6MWT, patients unable to perform the walk due to a medical reason will be considered to have walked an actual distance of zero.

Patient Preference Survey at baseline will be performed and reported by Edwards Global Health Economics and Reimbursement (GHER) separately.

Revision Date: Au		ugust 1, 2022	Rev	For Use Only by Affiliates of Edwards Lifesciences	Page 16 of 18
Edwards	Title	Statistical Analysis P	lan foi	CEND Study	(2019-06)

The number and percentage of patients who had clinically significant abnormal laboratory parameters (out of normal range) collected per protocol will be summarized at each visit.

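### Patients who die drop out of the functional change analyses while a patient too ill to walk scores 0 m, so survivor-only change may overstate benefit

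*SAP*

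**What the plan says.** SAP 8.4 covers the functional endpoints in the As-Treated population. For KCCQ, SF-36v2 and the 6-minute walk: "Change from baseline at corresponding follow-up visits will be summarized by mean and standard deviation", and then "Patients who are missing a baseline or follow up values will be excluded from the analysis". The next sentence makes one exception, for the walk only: "patients unable to perform the walk due to a medical reason will be considered to have walked an actual distance of zero". It names no visit.

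For NYHA class, body weight, ankle circumference and edema, the same section plans paired tests against baseline and states: "Patients who are missing a baseline or follow-up value will be excluded from the paired analysis".

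The general rules point the same way. SAP 6.2 limits analyses to patients with available data and, apart from adverse-event dates, says "no other missing value imputation will be performed". SAP 6.1 adds that, by default, "patients with missing data will be excluded from the denominator". Protocol 12.8 reads "All statistical analyses will be performed using only those patients with available data required for endpoint analysis", and Protocol 12.6 has the same complete-pair rule for quality of life: "Patients that are missing a baseline or follow up values will be excluded from the analysis".

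Neither document names death in any functional analysis. All-cause mortality is estimated separately by Kaplan-Meier at 12 months and annually (SAP 8.4).

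**The concern.** The 0 m rule treats medical inability to walk as a poor outcome, not as missing data. Death, the worse outcome, then falls under the missing-data rule. The most unfavourable walk change a patient can contribute is kept while the patient lives and removed when the patient dies. KCCQ, SF-36v2 and NYHA change have no counterpart to the 0 m rule and rest wholly on patients who are alive with both values.

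The study has one arm, so change from baseline is its evidence of functional benefit, and functional follow-up runs to 5 years. One stated objective is to guide the design of later studies, so these effect sizes may be carried forward. A reader of a late-visit mean needs to know how many treated patients it leaves out because they died, and what share of those due at the visit were alive and better.

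**Working it through.** The documents give no expected change, standard deviation, baseline distance or mortality, and SAP 2.3 gives no statistical basis for the sample size. There is no planned figure to reproduce. **All numerical inputs below are assumptions.** The values +30 m and +10 points are borrowed from the SAP 3.7.4 thresholds for illustration only.

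**Step 1: how each patient is handled at a follow-up visit**

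| Status at visit | 6-minute walk change | KCCQ, SF-36v2, NYHA change |
|---|---|---|
| Alive, value recorded | included | included |
| Alive, cannot walk for a medical reason | included, follow-up = 0 m | included if recorded |
| Dead | no follow-up value, pair excluded | no follow-up value, pair excluded |

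The last row is inferred from the missing-value rules; it is not stated.

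**Step 2: a patient scored 0 m later dies.** Let N = 150, walkers' change D = +40 m and baseline B = 200 m, with k patients unable to walk. While they live, mean change = ((N − k)·D − k·B)/N. After they die, it is D.

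| k | Alive, scored 0 m | After death |
|---|---|---|
| 5 | (145·40 − 5·200)/150 = +32 m | +40 m |
| 10 | (140·40 − 10·200)/150 = +24 m | +40 m |
| 20 | (130·40 − 20·200)/150 = +8 m | +40 m |

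The direction does not depend on these values. Removing a change of −B raises the mean whenever the other patients' mean change is above −B, which holds in any result that shows improvement.

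**Step 3: deaths in general.** Let m be the share dead, D the survivors' mean change and D_dec the change the decedents would have shown. Complete pairs give D; all patients would give (1 − m)·D + m·D_dec. The shift is m·(D − D_dec). With D = +30 m:

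| m | D_dec = −50 | 0 | +30 | +60 |
|---|---|---|---|---|
| 10% | +8 m | +3 m | 0 | −3 m |
| 20% | +16 m | +6 m | 0 | −6 m |
| 40% | +32 m | +12 m | 0 | −12 m |

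A simulation of 400,000 patients (baseline mean 220 m, SD 100 m; death likelier at low baseline; 20% dead; all-patient mean change about +30 m) gave these survivor means:
- 30.1 m when change was unrelated to baseline
- 33.5 m when patients with low baseline improved less
- 26.6 m when they improved more

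The sign depends on what the decedents would have done, because dropping a pair also removes the decedent's baseline.

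**Step 4: extending the SAP's own 0 m score to death.** The mean becomes (1 − m)·D − m·B, where B is now the decedents' mean baseline. With D = +30 m:

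| m | B = 150 m | 200 m | 250 m |
|---|---|---|---|
| 5% | +21.0 m | +18.5 m | +16.0 m |
| 10% | +12.0 m | +7.0 m | +2.0 m |
| 20% | −6.0 m | −16.0 m | −26.0 m |

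The mean reaches zero at m = D/(D + B): 16.7%, 13.0% and 10.7% dead. For KCCQ with D = +10, decedent baseline 40 and death scored 0, it is 0.9·10 − 0.1·40 = +5 at 10% dead and 0.8·10 − 0.2·40 = 0 at 20%. Complete pairs show +30 m and +10 points throughout. This is a benchmark for how much the unstated choice can matter; it is not the correct value.

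**The case against.** **A dead patient has no walk distance or KCCQ score.** A living patient who cannot walk does have a meaningful distance of zero. A while-alive summary set beside mortality is a recognised choice. This stands: treating the two differently is not in itself an error. What is missing is a statement that this is the choice, and an output that puts survival and function together.

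**Deaths are reported.** The plan has Kaplan-Meier mortality, causes of death at 30 days, 1 year and annually (SAP 9.1), disposition by visit (SAP 7.1) and the number of observations with each continuous summary (SAP 6.1). So deaths are not hidden. But none of these gives the share of treated patients who were alive and better. Exploratory Individual Patient Success (SAP 3.7.4) comes closest, since it requires NYHA, walk and KCCQ improvement together. It applies at 12 months only, its device-success element names only procedural mortality (SAP 3.7.2), and no rule says that a later death counts as failure.

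**The study is a feasibility study.** It has no stated functional success criterion, and exclusion criterion 33 keeps out patients with life expectancy under 12 months. This limits the weight of the point and argues against presuming heavy early loss.

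**A reader might infer that reported improvement must rise as the sickest patients die, and that the loss is large.** The documents support neither. Step 3 shows that the shift can be zero or negative, and no mortality or attrition figure is given. The mean age of 78 years in Protocol 7.1 comes from compassionate use and does not supply one.

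**Conclusion.** The point holds as a gap in the plan, worth correcting but not critical. As written, medical inability to walk counts as 0 m, while death removes the patient from every KCCQ, SF-36v2, walk and NYHA change analysis. The second half is an inference, but the missing-value rules leave no other reading.

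One consequence is certain: when a patient scored 0 m dies and others are unchanged, mean walk change rises in any result showing improvement. In the illustration the rise is 8 m, 16 m or 32 m for 5, 10 or 20 such patients among 150. Beyond that case, overstatement is possible but not established. It requires that decedents would have changed less than survivors, which is plausible but is not shown in either document. The real size cannot be given, because it depends on mortality, baseline values and changes that the documents do not supply.

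**What to change.** 1. State in SAP 8.4 that the paired means are conditional on survival. Keep them as planned, label them as being among survivors with paired data, and show the numbers died and the numbers alive with missing data beside each one.
2. At each visit, over all As-Treated patients due for that visit, add for each measure the proportion alive and improved by the SAP 3.7.4 thresholds: NYHA by at least 1 class, walk distance by at least 30 m, KCCQ by at least 10 points. Count death as not improved, and report patients alive with missing data separately. SF-36v2 has no threshold there, so item 1 is enough for it.
3. Add died as a category in the NYHA distribution table.

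A mixed model for repeated measures would not settle this. It implicitly projects values past death, which conflicts with a survivors label.

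The cost is a few extra table rows and no new data collection. The added proportions will look less favourable than the survivor means.

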8.11.4. Post-Procedure Therapy

8.11.4.1 Post-Implant Up to 6 Months

Recommendation for all patients: warfarin (target INR range 2.5-3.5) or other appropriate anticoagulant + acetylsalicylic acid (ASA, 75-100 mg) for up to the 6-month follow-up visit.

Post-implant for patients on warfarin therapy, the use of heparin as a bridging agent to warfarin therapy may be used until the INR stabilizes at 2.5 or greater. The use of home INR monitoring devices in addition to frequent assessment of INR by the treating physicians is recommended.

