11.3. Findings That Do Not Require Reporting to the Sponsor

For purposes of this study, the following findings are not considered adverse events, because of their nature, do not require reporting to the Sponsor. These findings are normally expected to occur in association with treatment of tricuspid regurgitation, and/or are associated with customary, standard care of patients undergoing transcatheter, cardiovascular procedures.

- Post-procedure pain (within 48 hour of procedure) not requiring treatment or treated with non-opioids
- Abnormal or out of range lab values (e.g., electrolyte imbalance) that are not clinically significant and do not require correction or treatment

Note: Abnormal lab values that roll up to a diagnosis should not be reported as separate AEs (e.g., elevated BNP in patient with heart failure; increased K+ in patient with renal insufficiency; elevated white blood count in a patient with a diagnosed infection).

- Low grade temperature increase without signs and symptoms of infection
- Minor, localized tenderness, swelling, induration, oozing, etc. at access site(s)
- Sinus bradycardia or tachycardia that does not require treatment or intervention
- Systolic or diastolic blood pressure changes that do not require treatment or intervention
- The need for insulin in a diabetic patient in the post-op period

This list of findings is intended to provide guidance to the study sites for the purpose of AE reporting. The Investigator should utilize his/her own clinical judgment in evaluating adverse experiences and may decide that the above findings should be reported as adverse events.

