#### 3.4 Clinical and Functional Endpoints and Parameters

- 3.4.1 Clinical and Functional Endpoints
  - The following endpoints will be assessed at 12 months and annually until 5 years post-procedure:
    - A. All-cause mortality
    - B. Heart failure hospitalizations
    - C. Non-elective tricuspid valve re-intervention, percutaneous or surgical
  - The following endpoints will be assessed at baseline, 30 days, 6 months, 12 months, and annually until 5 years post-procedure:
  - A. Volume overload assessed by serial measurements of:
    - 1. Body weight
    - 2. Edema assessment (1+ to 4+)
    - 3. Ankle circumference measurement
    - 4. Patient edema questionnaire
  - B. Functional class, functional status, and quality of life assessed by:
    - 1. New York Heart Association (NYHA) Classification
    - 2. 6-Minute Walk Test (6MWT)
    - 3. Kansas City Cardiomyopathy Questionnaire (KCCQ)
    - 4. Short Form Health Survey (SF-36v2)
- 3.4.2 Clinical and Functional Parameters
  - The following parameters will be assessed at baseline:
    - A. Canadian Study of Health and Aging (CSHA) Clinical Frailty Scale
    - B. Katz Index of Independence in Activities of Daily Living (Katz ADL)
    - C. Patient Preference Survey
  - The following general clinical and laboratory parameters will be assessed at discharge, 30 days, 6 months, 12 months, and annually until 5 years post-procedure:
    - A. Complete Blood Count (CBC)
    - B. Comprehensive Metabolic Panel (CMP)
    - C. Coagulation Panel (PT or PTT; INR for patients on vitamin K antagonist [VKA])
    - D. BNP(B-type natriuretic peptide) or NT-proBNP
    - E. GGT
    - F. Uric acid and eGFR

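### SAP 8.4 gives out of normal range as its only criterion for a clinically significant laboratory abnormality and plans per-visit counts with no paired comparison to baseline

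*SAP*

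**What the plan says.** SAP 8.4 gives laboratory results a single sentence, for the As-Treated population. At every visit it reports how many, and what share, are "patients who had clinically significant abnormal laboratory parameters (out of normal range) collected per protocol". No grade, threshold or assessor follows.

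SAP 3.4.2 lists what is covered: blood count, metabolic panel, coagulation panel (with INR for patients on a vitamin K antagonist), BNP or NT-proBNP, GGT, uric acid and eGFR. On timing it says: "The following general clinical and laboratory parameters will be assessed at discharge, 30 days, 6 months, 12 months, and annually until 5 years post-procedure". Baseline is not in that list, yet Protocol Tables 7 and 14 schedule every one of these tests at screening/baseline.

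Two protocol passages bear on the meaning of the SAP sentence. Protocol 11.3, on findings that sites need not report, includes "Abnormal or out of range lab values (e.g., electrolyte imbalance) that are not clinically significant and do not require correction or treatment", and gives "elevated BNP in patient with heart failure" as an example of an abnormal value that belongs to a diagnosis. Protocol 8.11.4.1 recommends "warfarin (target INR range 2.5-3.5) or other appropriate anticoagulant", together with aspirin, for up to the 6-month visit.

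**The concern.** There are two linked weaknesses.

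First, the label. The SAP puts a range criterion next to a term that the protocol uses for something narrower. A programmer who takes the bracket as the definition would produce a table headed clinically significant that also holds values at their treatment target and values explained by the disease under study.

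Second, the comparison. This is a single-arm study, so for laboratory values the only available reference is the patient's own baseline. A count at each visit, without pairing, does not say whether an abnormality appeared after the device, was there before it, or improved while staying outside the range. The study's stated objectives are to evaluate safety and to guide later designs, and a laboratory table that cannot make that distinction serves them poorly.

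**Working it through.** The documents give no figure for this point, so there is none to reproduce. The check compares passages, with three small illustrations whose assumptions are stated.

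**1. The criterion.** SAP 8.4 supplies one operational test, the bracket. Protocol 11.3 describes values that are out of range and not clinically significant, so the protocol does not treat the two as equivalent. The SAP sentence has two readings:
- *Literal:* the bracket defines the whole phrase, and every out-of-range value qualifies.
- *Narrow:* the bracket explains only *abnormal*, and *clinically significant* is a further condition that is not defined.

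**2. INR on the literal reading.** The protocol's warfarin target is 2.5-3.5. The documents give no normal range for INR. With an assumed upper normal limit between 1.1 and 2.0, the bottom of the target is 2.5/1.1 = 2.27 to 2.5/2.0 = 1.25 times that limit. Every on-target value would then be out of range, and better control would raise the abnormal count. This applies only to patients on a vitamin K antagonist.

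**3. Chance flags on the literal reading.** About 13 analytes are named: seven in the metabolic panel, plus platelets, a coagulation test, a natriuretic peptide, GGT, uric acid and eGFR. Assume independent tests and reference intervals that leave out 2.5% to 5% of healthy people. The chance of at least one out-of-range value at a visit is 1 - (1 - a)^13:
- a = 0.025 gives 28%
- a = 0.05 gives 49%

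This matters only if the table counts patients with any abnormal parameter; the sentence does not say whether it is per parameter. Tests on one sample are correlated, so these figures are indicative only.

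**4. Abnormality before the device.** Protocol 7.3 excludes eGFR of 25 or below, hemoglobin below 9 g/dL not corrected by transfusion, platelets below 75,000 and Child-Pugh class C. It therefore admits eGFR just above 25, hemoglobin from 9 g/dL, platelets from 75,000 and Child-Pugh classes A and B.

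**5. Where the SAP plans a baseline comparison.**
- Shift from baseline with a paired test: NYHA class, body weight, ankle circumference, edema (SAP 8.4).
- Change from baseline: KCCQ, SF-36v2, 6-minute walk (SAP 8.4) and the echocardiographic variables (SAP 8.3).
- Laboratory values: none. SAP 6.1 offers change from baseline only for selected endpoints and does not name them; SAP 7.2 lists no laboratory value among baseline characteristics; Protocol section 12 has no laboratory analysis.

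**6. What unpaired counts leave open.** Take n patients measured at both visits, a out of range at baseline and b at follow-up. The number newly out of range lies anywhere from max(0, b - a) to min(b, n - a). If a = b, the two counts look like no change. With n = 200, the planned maximum, and a = b = 100 (an assumption, chosen as the widest case), the number newly abnormal could be anything from 0 to 100. A baseline column in the same table would not close this gap; only pairing within patients does.

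**The case against.** The strongest reply is that the sentence is ambiguous rather than wrong. A reader might infer that the SAP treats every out-of-range value as clinically significant, so that on-target INR and expected BNP are certain to be counted. The documents do not support that. On the literal reading the words *clinically significant* would add nothing, and Protocol 11.3 uses the two terms separately, which fits the narrow reading equally well. What stands is that the narrow reading leaves the term undefined, so the sentence needs repair either way.

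A reader might put a size on the INR and BNP effect. The documents do not say how many patients take warfarin, since another anticoagulant is allowed, or how many have a raised BNP at entry. No percentage can be defended.

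A reader might also infer that laboratory harm would go unseen. It would not:
- Values that are clinically significant or need treatment fall outside the Protocol 11.3 exemption.
- Clinically significant worsening of a pre-existing condition must be recorded as an adverse event (Protocol 11.4).
- SAP 9.2 summarizes and lists adverse events.
- Unplanned dialysis or renal replacement is a component of the major adverse event composite.
- Stage 2 or 3 acute kidney injury counts against Exploratory Procedural Success (SAP 3.7.3).

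Nor do the visible documents claim a renal or hepatic improvement that the table would hide; the section on potential benefits is redacted. No passage plans to pool BNP with NT-proBNP. Keeping them apart becomes necessary only once a continuous change is reported.

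It can also be said that SAP 6.1 provides general descriptive statistics for continuous variables at each assessment, and that each visit may include baseline. Both are fair readings. Neither promises a paired or shift comparison for laboratory values.

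**Conclusion.** The point holds in limited form. *Out of normal range* is the only criterion that SAP 8.4 gives for a clinically significant laboratory value, and it blurs a distinction that the protocol makes. Whether on-target INR and the BNP of heart failure would be counted depends on how the bracket is read. The firmer finding does not depend on that: no paired comparison with baseline is specified, although the baseline samples exist, the entry criteria admit abnormal values, and the same SAP section plans such comparisons for its other measures.

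The size is modest. This is a descriptive summary of parameters in a feasibility study. It feeds neither the 30-day major adverse event endpoint nor device, procedural or clinical success. The chance-flag, INR and pairing figures are illustrations under the stated assumptions, not estimates for this trial. The change is a cheap improvement, not a condition for the study to be interpretable.

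**What to change.** Revise the laboratory sentence in SAP 8.4 as follows:

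1. Label values flagged by range alone as *outside the reference range*, and state that the range is that of the local laboratory reporting the result. Keep *clinically significant* for values that the investigator judged so or that led to an adverse event. If the database holds no such judgment for each result, use the adverse event link alone.
2. For each parameter, tabulate the shift from baseline (in range / out of range) at each visit, using the baseline values already collected, and count new abnormalities separately. Add baseline to the laboratory time points in SAP 3.4.2.
3. Summarize INR in patients on a vitamin K antagonist as below, within or above the protocol's stated target range. This is a presentation choice and alters no treatment recommendation.
4. Give change from baseline for key continuous values, such as eGFR, bilirubin and GGT. Report BNP and NT-proBNP separately, pairing visits only within the same assay.

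The cost is SAP wording and a few extra descriptive tables. No new test or visit is needed.
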